3.2.2 Progression free survival (PFS)

PFS is defined as the time from randomisation until the date of objective disease progression or death (by any cause in the absence of progression) regardless of whether the patient withdraws from randomised therapy or receives another anti-cancer therapy prior to progression (i.e. date of PFS event or censoring – date of randomisation + 1). Patients who have not progressed or died at the time of analysis will be censored at the time of the latest date of assessment from their last evaluable RECIST assessment. However, if the patient progresses or dies immediately after two or more consecutive missed visits, the patient will be censored at the time of the latest evaluable RECIST 1.1 assessment prior to the two missed visits (Note: NE visit is not considered as missed visit).

Given the scheduled visit assessment scheme (i.e. six-weekly for the first 24 weeks then eight-weekly thereafter) the definition of 2 missed visits will change, as follows and summarised in [Table 6](#).

- If the previous RECIST assessment is less than study day 134 (i.e. week 19) then two missing visits will equate to 14 weeks since the previous RECIST assessment, allowing for early and late visits (i.e. $2 \times 6 \text{ weeks} + 1 \text{ week for an early assessment} + 1 \text{ week for a late assessment} = 14 \text{ weeks}$).
- If the two missed visits occur over the period when the scheduled frequency of RECIST assessments changes from six-weekly to eight-weekly this will equate to 16 weeks (i.e. $6 \text{ weeks} + 8 \text{ weeks} + 1 \text{ week for an early assessment} + 1 \text{ week for a late assessment} = 16 \text{ weeks}$). The time period for the previous RECIST assessment will be from study days 134 to 168 (i.e. week 20 to week 24).
- From week 25 onwards (when the scheduling changes to eight-weekly assessments), two missing visits will equate to 18 weeks (i.e. $2 \times 8 \text{ weeks} + 1 \text{ week for an early assessment} + 1 \text{ week for a late assessment} = 18 \text{ weeks}$).

Table 6 Definition of Two Missed Visits

Scheduled assessment	Previous assessment scan	Two missed visits window
Week 7	No evaluable scan or no screening scan	2 x 6 weeks + 2 weeks = 14 weeks (98 days) (relative to randomisation)
Week 7	Screening scan	2 x 6 weeks + 2 weeks = 14 weeks (98 days) (relative to randomisation)
Q6W up to Week 25	> Day 1 – Day 133 (up to Week 19)	2 x 6 weeks + 2 weeks = 14 weeks (98 days)
	> Day 133 – Day 168 (Week 20 – Week 24) (change period from Q6W to Q8W)	6 weeks + 8 weeks + 2 weeks = 16 weeks (112 days)
Q8W thereafter	Day 169 onwards (Week 25 onwards)	2 x 8 weeks + 2 weeks = 18 weeks (126 days)

If the patient has no evaluable visits or does not have baseline data, they will be censored at Day 1 unless they die within two visits of baseline (12 weeks plus 1 week allowing for a late assessment within the visit window).

The PFS time will always be derived based on scan/assessment dates, not visit dates.

RECIST assessments/scans contributing towards a particular visit may be performed on different dates. The following rules will be applied:

- For BICR assessments, the date of progression will be determined based on the **earliest** of the scan dates of the component that triggered the progression for the adjudicated reviewer selecting PD or of the reviewer who read baseline first if there is no adjudication for BICR data.
- For investigational assessments, the date of progression will be determined based on the **earliest** of the dates of the component that triggered the progression.
- For both BICR and investigational assessments, when censoring a patient for PFS the patient will be censored at the **latest** of the dates contributing to a particular overall visit assessment.

Note: for TLs only the latest scan date is recorded out of all scans performed at that assessment for the TLs and similarly for NTLs only the latest scan date is recorded out of all scans performed at that assessment for the NTLs.

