3 PRIMARY AND SECONDARY VARIABLES

3.1 Derivation of RECIST Visit Responses

For all patients, the RECIST tumour response data will be used to determine each patient's visit response according to RECIST version 1.1. It will also be used to determine if and when a patient has progressed in accordance with RECIST and their best objective response to study treatment.

Baseline radiological tumour assessments are to be performed no more than 28 days before the start of randomised treatment and ideally as close as possible to the start of study treatment.

For patients who cross-over to savolitinib plus osimertinib based on confirmed objective disease progression during the initial randomised treatment period (including patients who have already crossed over based on confirmed PD prior to CSP V3.0) the baseline scan for response endpoints during the cross-over period will be the progression scan on savolitinib plus placebo, which should be acquired within 28 days of the start of treatment in the cross-over period. Scheduled RECIST 1.1 tumour assessments are not required for these patients, and the subsequent assessment of disease progression will be based on standard-of-care scan or investigator determined clinical progression.

For patients who cross-over after study unblinding and who have not objectively progressed during the initial randomised treatment period, scheduled RECIST 1.1 tumour assessments are

required using initial randomisation as baseline. Patients who then discontinue study intervention after cross-over for reasons other than investigator-confirmed disease progression will continue scheduled RECIST 1.1 tumour assessments until objective disease progression per RECIST 1.1 as assessed by investigator, unless they withdraw consent to the entire study. These tumour assessments are then performed every 6 weeks following the start of study treatment up to 24 weeks relative to initial randomisation, then every 8 weeks until objective disease progression.

If an unscheduled assessment is performed, and the patient has not progressed, every attempt should be made to perform the subsequent assessments at their scheduled visits. This schedule is to be followed in order to minimise any unintentional bias caused by some patients being assessed at a different frequency than other patients.

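### The two-missed-visits limits for PFS are attached to the wrong previous-scan days around the change from 6-weekly to 8-weekly scans, so some patients who missed one scan are censored as if they had missed two

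*SAP*

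**What the plan says.** Section 3.2.2 describes the scan schedule as "six-weekly for the first 24 weeks then eight-weekly thereafter". If a patient progresses or dies straight after at least two missed scans in a row, PFS is censored at the last evaluable scan before the gap. The length that counts as two missed scans depends on the previous scan:

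- **14 weeks (98 days).** "If the previous RECIST assessment is less than study day 134 (i.e. week 19) then two missing visits will equate to 14 weeks". Table 6 puts every previous scan up to Day 133 here.
- **16 weeks (112 days).** This is meant for two missed visits that straddle the change from 6-weekly to 8-weekly scans. "The time period for the previous RECIST assessment will be from study days 134 to 168 (i.e. week 20 to week 24").
- **18 weeks (126 days).** Previous scan on Day 169 or later.

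Each limit is the sum of the two scheduled intervals, plus one week for an early scan and one for a late scan.

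For patients with no usable scan ("No evaluable scan or no screening scan"), and for those with only a screening scan, Table 6 gives 98 days from randomisation. The paragraph below the table uses Day 1 as the censoring date for patients with no evaluable visit or no baseline data, with one exception: "unless they die within two visits of baseline (12 weeks plus 1 week allowing for a late assessment within the visit window"). Section 3.2.5 uses 91 days after randomisation for the matching BoR rule.

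**The concern.** The three lengths are right, but the day bands do not match the visits that follow each scan. The only two consecutive visits that straddle the change are weeks 24 and 32, and the scan before them is week 18. That scan falls almost wholly in the 14-week band. The 16-week band lies between the nominal week-18 and week-24 days and contains no nominal scan day.

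If the limit is too short, a patient who missed one scan is treated as having missed two. The event is dropped and the patient is censored at the earlier scan. This carries into PFS by investigator and by BICR (Section 4.2.3.1), and into DoR, which ends on the PFS date (Section 3.2.3). Section 4.2.3.1 estimates the hazard ratio only if there are at least 20 events, and recruitment stopped early, so lost events could matter if the count is close to 20.

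**Working it through.** **Inputs, all from the SAP.** Scans every 6 weeks to week 24, then every 8 weeks (Section 3.2.2). Windows of ±7 days (the early and late allowances in Section 3.2.2; ±1 week in Section 3.2.6). Randomisation is Day 1, since PFS is "date of PFS event or censoring – date of randomisation + 1". So nominal day = 7 × week + 1, and weeks 6, 12, 18, 24, 32, 40 and 48 are Days 43, 85, 127, 169, 225, 281 and 337. Table 6 agrees: it calls the first scan Week 7 and starts Week 25 on Day 169.

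**The plan's lengths reproduce.** 6+6+2 = 14 weeks = 98 days; 6+8+2 = 16 weeks = 112 days; 8+8+2 = 18 weeks = 126 days.

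**The bands do not.** Limit needed = the next two intervals + 14 days.

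| Previous scan (window) | Next two visits | Needed | SAP gives |
|---|---|---|---|
| Week 6 (36-50) | 12, 18 | 98 | 98 |
| Week 12 (78-92) | 18, 24 | 98 | 98 |
| Week 18 (120-134) | 24, 32 | 112 | 98 on Days 120-133; 112 on Day 134 |
| Week 24 (162-176) | 32, 40 | 126 | 112 on Days 162-168; 126 from Day 169 |
| Week 32 (218-232) | 40, 48 | 126 | 126 |

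**Examples with one missed scan.**
- Scan Day 127, week 24 missed, progression Day 226: 226 − 127 = 99 > 98, so censored at Day 127.
- Scan Day 168, week 32 missed, progression Day 281: 281 − 168 = 113 > 112, so censored at Day 168.
- Death after a Day 127 scan: 127 + 98 = 225, so a death on Days 226-232 is censored, although the week-32 window is open until Day 232.

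**How often, given that one scan is missed and progression is found at the next.** Take all 15 × 15 = 225 in-window day pairs, equally weighted (an assumption), and censor when the gap exceeds the limit.
- Week 18 to week 32: the nominal gap is exactly 98 days, so a pair is censored when the later scan's offset exceeds the earlier one's: (225 − 15)/2 = 105, and 105/225 = 47%.
- Week 24 to week 40: only previous scans on Days 162-168 count: 14+13+12+11+10+9+8 = 77, and 77/225 = 34%. Among those early scans it is 77/(7 × 15) = 73%.
- Previous scan at week 6, 12 or 32: 0/225.

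If a gap equal to the limit also counts, the two figures are 119/225 (53%) and 84/225 (37%). If the nominal day is 7 × week, with the gap required to exceed the limit, they are 105/225 and 84/225. With scans within ±3 days they are 21/49 and 15/49. No pair errs the other way: every gap with two missed scans is caught.

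**Distance moved.** Wrongly censored gaps are 99-112 days after week 18 and 113-126 days after week 24, so censoring falls about 14 to 18 weeks before the event.

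**Corrected bands.** With cut-points at Days 119 and 161, 0/225 one-missed-scan pairs are censored for every previous scan in the table, and every two-missed-scan pair tested is still caught. Only Days 120-133 (14 to 16 weeks) and Days 162-168 (16 to 18 weeks) change.

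**Baseline rows.** Table 6: 2 × 42 + 14 = 98 days. Text: 12 × 7 + 7 = 91 days, the BoR figure. Randomisation is a fixed date, so no early-scan week is needed. A death 92 to 98 elapsed days after randomisation, with no evaluable visit, is inside the Table 6 window but censored at Day 1 by the text.

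**The case against.** The best case against is about scope. Most of the rule is right. Scans exactly on schedule give a gap of 98 days, which does not exceed 98. An error needs a patient who attends week 18, or an early week 24, misses one particular visit, and then progresses or dies at an unlucky offset. Assume 56 patients (the original target, so an upper bound), 60% and 50% still at risk at weeks 18 and 24, 30% progressing in the gap, and 2-10% missing the visit; none of these four percentages is in the SAP. The expected number of progressions affected is then 56 × 0.30 × (0.60 × 0.467 + 0.50 × 0.342) × (0.02 to 0.10), about 0.15 to 0.8. PFS is secondary, ORR does not use these limits, and Section 4.2.1 plans no inferential analyses. All of this stands and limits the severity. It does not remove the contradiction between rule and bands.

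A second objection is that the corrected limit lets some deaths through: after a Day 127 scan with weeks 24 and 32 missed, a death on Days 233-239 is kept as an event (127 + 112 = 239). That is true, but it comes from the SAP's own two-week allowance and occurs in the correct rows too: after a Day 43 scan with weeks 12 and 18 missed, a death on Days 135-141 is kept (43 + 98 = 141).

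A reader might infer that every limit is one visit out of step, that 47% and 34% are shares of trial patients, or that the hazard ratio will be lost or biased in a known direction. The SAP supports none of these. The misassignment is confined to Days 120-133 and 162-168, the percentages are conditional, and no event count or split by arm is given.

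**Conclusion.** The bands are wrong as written and should be corrected, though this is not a critical defect. Section 3.2.2 and Table 6 contradict their own rule for week-18 scans up to Day 133 and for week-24 scans on Days 162-168. Some patients who missed one scan are therefore censored 14 to 18 weeks before their event. The 47% and 34% rest on evenly spread scan days and on exactly that one scan being missed. The number of patients is likely small. The error only removes events, from PFS by both assessors and from DoR, and its effect on the 20-event threshold is a possibility only. The SAP does not say whether a gap must exceed the limit or may equal it, and on-schedule week-18 to week-32 gaps turn on that. The conflict between 98 and 91 days is separate and minor: it concerns deaths in a single week among patients with no evaluable visit or no baseline data.

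**What to change.** 1. In the three bullets of Section 3.2.2 and in Table 6, set the previous-scan bands to: up to Day 119, 14 weeks; Days 120-161, 16 weeks; Day 162 onwards, 18 weeks. In Table 6's week numbering (Week n ends on Day 7n) the labels become up to Week 17, Weeks 18-23, and Week 24 onwards.
2. State that the gap must exceed the limit. Under an equal-or-exceed reading, even a correct row censors one in-window pair in 225 after a single missed scan.
3. Set the two baseline rows of Table 6 to 91 days after randomisation, stated as elapsed days (study Day 92), so that they agree with the text below the table and with Section 3.2.5. Read as study day 91, a permitted late week-12 scan on Day 92 would fall outside.

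The cost is an edit to three bullets, the rows and week labels of Table 6, and the PFS derivation, which DoR and PFS per BICR then inherit. No new data are needed.

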3.2.3 Duration of response (DoR)

DoR will be defined as the time from the date of first documented response until date of documented progression or death in the absence of disease progression (i.e. date of PFS event or censoring – date of first response + 1). The end of response should coincide with the date of progression or death from any cause used for the PFS endpoint. The time of the initial response will be defined as the latest of the dates contributing towards the first visit response of PR or CR.

If a patient does not progress following a response, then their DoR will use the PFS censoring time.

3.2.4 Overall survival (OS)

Overall survival is defined as the time from the date of randomisation until death due to any cause regardless of whether the patient withdraws from randomised therapy or receives another anti-cancer therapy (i.e. date of death or censoring – date of randomisation + 1). Any patient not known to have died at the time of analysis will be censored based on the last recorded date on which the patient was known to be alive (SUR_DAT, recorded within the SURVIVE module of the eCRF).

Note: Survival calls will be made in the week following the date of data cut-off (DCO) for the analysis, and if patients are confirmed to be alive or if the death date is post the DCO date these patients will be censored at the date of DCO. The status of ongoing, withdrawn (from the study) and “lost to follow-up” patients at the time of the final OS analysis should be obtained by the site personnel by checking the patient’s notes, hospital records, contacting the patient’s general practitioner and checking publicly-available death registries. In the event that the patient has actively withdrawn consent to the processing of their personal data, the vital status of the patient can be obtained by site personnel from publicly available resources where it is possible to do so under applicable local laws.

Note: For any OS analysis performed prior to the final OS analysis, in the absence of survival calls being made, it may be necessary to use all relevant CRF fields to determine the last recorded date on which the patient was known to be alive for those patients still on treatment (since the SURVIVE module is only completed for patients off treatment if a survival sweep is not performed). The last date for each individual patient is defined as the latest among the following dates recorded on the CRFs:

- AE start and stop dates
- Admission and discharge dates of hospitalization
- Study treatment date
- End of treatment date
- Laboratory test dates

- Date of vital signs
- Disease assessment dates on RECIST CRF
- Start and stop dates of alternative anticancer treatment
- Date last known alive on survival status CRF
- End of study date.

If a patient is known to have died where only a partial death date is available, then the date of death will be imputed as the latest of the last date known to be alive + 1 from the database and the death date using the available information provided:

- a. For Missing day only – using the 1st of the month
- b. For Missing day and Month – using the 1st of January

If there is evidence of death but the date is entirely missing, it will be treated as missing, i.e. censored at the last known alive date.

3.2.5 Best objective response (BoR)

Best objective response (BoR) is calculated based on the overall visit responses from each RECIST assessment, described in [Section 3.1.3](#). It is the best response a patient has had following randomisation, but prior to starting any subsequent cancer therapy and up to and including RECIST progression or the last evaluable assessment in the absence of RECIST progression. Categorisation of BoR will be based on RECIST using the following response categories: CR, PR, SD, NED (applies only to those patients entering the study with no disease at baseline), PD and NE.

For determination of a best response of SD, the earliest of the dates contributing towards a particular overall visit assessment will be used. SD should be recorded at least 6 weeks minus 1 week, i.e. at least 35 days (to allow for an early assessment within the assessment window), after randomisation. For CR/PR, the initial overall visit assessment that showed a response will use the latest of the dates contributing towards a particular overall visit assessment.

BoR will be determined programmatically based on RECIST from the overall visit response using all BICR data up until the first progression event. It will also be determined programmatically based on RECIST using all site investigator data up until the first progression event. The denominators for each case will be consistent with those used in the ORR analysis.

For patients whose progression event is death, BoR will be calculated based upon all evaluable RECIST assessments prior to death.

For patients who die with no evaluable RECIST assessments, if the death occurs ≤ 91 days (i.e. $[2 \times 6 \text{ weeks}] + 1 \text{ week}$ to allow for a late assessment within the assessment window) after randomisation, then BoR will be assigned to the progression (PD) category. For patients who die with no evaluable RECIST assessments, if the death occurs > 91 days after randomisation then BoR will be assigned to the NE category.

A patient will be classified as a responder if the RECIST criteria for a CR or PR are satisfied at any time following randomisation, prior to RECIST progression and prior to starting any subsequent cancer therapy.

3.2.6 Change in TL tumour size

The percentage change from baseline in TL tumour size at 12 weeks is based on RECIST TL measurements taken at baseline and at week 12. Tumour size is the sum of the longest diameters of the TLs. TLs are measurable tumour lesions. Baseline for RECIST is defined to be the last evaluable assessment prior to randomisation. The percentage change in TL tumour size at week 12 will be obtained for each patient taking the difference between the sum of the TLs at week 12 and the sum of the target lesions at baseline divided by the sum of the TLs at baseline times 100 (i.e. $[(\text{week 12} - \text{baseline}) / \text{baseline}] \times 100$).

Patients who progress before week 12 and enter the cross-over period of the study should have had a tumour assessment performed at the time of progression. The tumour size from their latest progression assessment will be used instead of a week 12 assessment.

No imputation will be used for summaries of the percentage change in tumour size from baseline by visit, but for summaries of the percentage change at week 12, imputation will be used.

TL imputation

For patients who have less than or equal to one-third of TLs missing (because of intervention) at week 12, assessment data from missing lesions will be scaled up proportionally to the sum of the corresponding lesions at baseline to give an estimated sum of diameters as described in Section 3.1.1.

Apply a window around the week 12 visit

Whenever TL tumour size data for the week 12 visit is available then this should be used in the analysis (Note: or the visit at which progression was documented if before week 12). The windowing rules detailed in CSP Section 1.3 will be used to assign the RECIST scan results to the visit; therefore, any RECIST scan performed within ± 1 week of the protocol scheduled visit will be used for that visit.

Best percentage change

The absolute change and percentage change from baseline in the sum of tumour size at each assessment will be calculated. The best change in tumour size (i.e. depth of response) is the largest decrease from baseline or the smallest increase from baseline in the absence of a reduction and will include all assessments prior to the earliest of death in the absence of progression, any evidence of progression, the start of subsequent anti-cancer therapy or the last evaluable RECIST assessment if the patient has not died, progressed or started subsequent anti-cancer therapy.

If best percentage change cannot be calculated due to missing data (including if the patient has no TLs at baseline), a value of + 20% will be imputed as the best percentage change from baseline in the following situations (otherwise best percentage change will be left as missing):

- If a patient has no post-baseline assessment and has died
- If a patient has new lesions or progression of NTLs or TLs
- If a patient has withdrawn due to PD and has no evaluable TL data before or at PD.

3.3 Safety Variables

3.3.1 Exposure and dose interruptions

Exposure (i.e. duration of treatment) will be defined for both savolitinib and osimertinib/placebo as follows:

Total (or intended) exposure of study treatment

- Total (or intended) exposure = $\min(\text{last dose date where dose} > 0 \text{ mg, date of death, date of DCO}) - \text{first dose date} + 1$

Actual exposure of study treatment

- Actual exposure = intended exposure – total duration of dose interruptions, where intended exposure will be calculated as above, and a dose interruption is defined as any length of time where the patient has not taken any of the planned daily dose.

The actual exposure calculation makes no adjustment for any dose reductions that may have occurred.

Number of treatment cycles received

Exposure will also be measured by the number of cycles received. A cycle corresponds to a period of 28 days. If a cycle is prolonged due to toxicity, this should still be counted as one cycle. A cycle will be counted if treatment is started even if the full dose is not delivered.

Missed or forgotten doses

Missed and forgotten doses should be recorded on the DOSE module as a dose interruption with the reason recorded as “Subject forgot to take dose”. These missed or forgotten doses will not be included as dose interruptions in the summary tables, but the information will appear in the listing for dosing. However, these missed and forgotten doses will be considered in the derivation of actual exposure.

Patients who permanently discontinue during a dose interruption

If a patient permanently discontinues study treatment during a dose interruption, then the date of last administration of study medication recorded on DOSDISC will be used in the programming.

Safety follow-up

- Total Safety Follow-up = $\min(\text{last dose date} + 28 \text{ days}, \text{date of withdrawal of consent}, \text{date of death}, \text{date of DCO}) - \text{first dose date} + 1$

